Data on study specific characteristics included dates of admission and discharge, diagnosis, details of surgery undergone, details of morbidity using Clavien-Dindo classification and mortality. Details of CPET and its measures as well as P-POSSUM scores were collated.

CPET specific data collected:

- 1) Exercise induced ST ischaemia- yes/no
- 2) VO₂ peak: actual and predicted
- 3) Anaerobic threshold:
- 4) VE/VCO₂:
- 5) Pulmonary function test- normal/ obstructive/ restrictive
- 6) Duration of pedalling bike
- 7) 30 day predicted risk

3. Outcome Measures:

Primary Outcome measures:

Primary outcome was measured in terms of CPET/P-POSSUM predicted mortality compared to actual 30 day mortality.

- In-hospital mortality
- 30 days
- 90 days

Secondary outcome measures:

Secondary outcome was measured in terms of CPET/ P-POSSUM predicted morbidity compared to actual morbidity (Clavien-Dindo grade 3 and above).

Morbidity in terms of:

- Post-operative pancreatic fistula
- Biliary fistula
- Delayed gastric emptying
- Bleeding
- Intra-abdominal collection
- Renal failure
- Cardiac complications
- Pulmonary complications
- Pulmonary embolism /DVT

The occurrence of morbidity and mortality were measured in terms of numbers and percentages. The calculated risk of morbidity and mortality by CPET and P-POSSUM are in terms of percentages, ranging from 0 to 100%, higher the percentage leading to worse outcome.

Statistical analyses overview:

The baseline characteristics were analysed using percentages and frequencies (mean, median, mode, standard deviation). Chi-square test was used to assess if the two study groups were

comparable. The p-value calculated was considered significant if <0.05 and confidence interval of 95%.

The study specific measures were analysed using parametric and non-parametric tests and binary logistic regression analyses to compare predicted to actual mortality and morbidity, between the participants who have had CPET and those who have not.

Univariate and multivariate analysis were done to assess if CPET measures could be used to predict occurrence of post-operative complications and morbidity.

4. Adverse Event information:

This was a retrospective review of a prospectively maintained database.

No adverse events were overcome during the time of the study

5. Limitations and Caveat:

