This was a retrospective review of a prospectively maintained database. The participants who underwent CPET was small compared to participants who did not. A prospective study with a large sample size is required to obtain more reliable results.

6. Certain Agreements:

All PIs are employees of Sponsor.

There is no specified results disclosure agreement between the PIs and sponsor.

7. Results Point of Contact

Name: Miss [name] (Principal Investigator)

Organization Name: East Lancashire Hospitals NHS Trust

[contact]

Email Id: [contact]

8. Results of the study

143 participants had Pancreatoduodenectomy during the study period. CPET was performed in 30 participants (21%). The participants' age was 67 ± 9 (Mean \pm SD). Forty participants (28.2%) had developed intra-abdominal collection (Clavien-Dindo III). In the CPET subgroup, Anaerobic Threshold (AT) ≤ 14 on CPET was a risk factor to develop intra-abdominal collection, according to univariate analysis (60% Vs 9%, p-value 0.02) and multivariate analysis (HR 3.5, 95% CI 1.6-657, p-value 0.02). Another significant risk factor was post-operative pancreatic leak (POPF) (40% Vs 22%, p-value 0.04).

By this study we concluded that participants who have Anaerobic Threshold ≤ 14 on CPET, are more likely to develop intra-abdominal collection requiring drainage after Pancreatoduodenectomy. This group of participants will be less likely to start chemotherapy early.

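### The ratio reported for AT ≤ 14 (HR 3.5) does not fit its own interval (1.6–657) or p-value, and an exploratory subgroup finding is worded as established

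*Combined protocol and SAP*

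**What the plan says.** The document is a combined plan and results summary. Under *CPET specific data collected*, anaerobic threshold (AT) is one of seven items and is entered only as "3) Anaerobic threshold", with no unit, category or cut-off. Item 3 (Outcome Measures) lists intra-abdominal collection as one of nine kinds of morbidity. The *Statistical analyses overview* calls p < 0.05 significant. It names binary logistic regression for comparing predicted with actual outcomes between the CPET and non-CPET groups. A separate sentence says that univariate and multivariate analyses assessed CPET measures as predictors of complications; it names no model, covariates, designated measure or multiplicity adjustment.

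Item 8 (Results of the study) says "CPET was performed in 30 participants (21"%). In that subgroup AT ≤ 14 is reported as a risk factor for collection by "univariate analysis (60% Vs 9%, p-value 0.02) and multivariate analysis (HR 3.5, 95% CI 1.6-657, p-value 0.02"). The conclusion follows: "participants who have Anaerobic Threshold ≤ 14 on CPET, are more likely to develop intra-abdominal collection requiring drainage after Pancreatoduodenectomy". Next comes "This group of participants will be less likely to start chemotherapy early", with no figure.

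Item 5 (Limitations and Caveat) notes the retrospective design and the small CPET group, and adds: "A prospective study with a large sample size is required to obtain more reliable results".

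**The concern.** A ratio from a regression model should sit near the middle of its confidence interval on the log scale. Here 3.5 lies close to the lower limit of 1.6 and very far from the upper limit of 657. This is the effect size behind the study's stated conclusion about AT, so an error in it matters.

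The value 14 also first appears in the results. The plan describes a general look at CPET measures against complications at the 5% level, and one pairing becomes the conclusion. If several pairings were tested, or if 14 was chosen after seeing the data, p = 0.02 does not carry its usual meaning. A reader could take away both a misprinted effect and a threshold of unknown origin as if it were ready for use.

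**Working it through.** **Inputs** (item 8): ratio 3.5; 95% limits 1.6 and 657; p = 0.02; rates 60% and 9%; 30 CPET participants. From the plan: seven CPET items, nine complications, significance at p < 0.05. I assume two-sided tests and a Wald interval, that is, one symmetric on the log scale.

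**1. Can the printed ratio be reproduced from its interval?** No.
- Centre: √(1.6 × 657) = 32.4. Rounding of the limits allows 31.9 to 32.9.
- Standard error of the log ratio: ln(657/1.6)/3.92 = 1.535.
- Test at the centre: z = ln(32.4)/1.535 = 3.479/1.535 = 2.27, p = 0.023. This agrees with the printed 0.02.
- Test at 3.5: z = ln(3.5)/1.535 = 1.253/1.535 = 0.82, p = 0.41, with interval 0.17 to 70.9. This agrees with neither the printed interval nor the printed p.
- Size of the discrepancy: 32.4/3.5 = 9.3.

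**2. Does a simple slip explain it?**
- Upper limit 6.57: centre 3.24, p = 0.001.
- Upper limit 65.7: centre 10.3, p = 0.014.
- Ratio 3.5 with lower limit 1.6: the upper limit would be 3.5²/1.6 = 7.66, p = 0.002.
- Ratio 3.5 with p = 0.02: the interval would be about 1.2 to 10.1.
- 3.5 as the log coefficient: ln(32.4) = 3.48, which rounds to 3.5. This reconciles all three figures, but it is an inference to confirm from the model output.

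**3. Could a non-Wald, asymmetric interval explain it?** On the log scale 3.5 is 0.78 above the lower limit and 5.23 below the upper, a ratio of 6.7. For comparison, the exact interval for a table of 6/10 vs 1/11 (odds ratio 15, interval 1.07 to 757) has distances 2.64 and 3.92, a ratio of 1.5. Asymmetry of that order does not explain the printed figures.

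**4. Crude effect.** The odds ratio from the rates is (0.60/0.40)/(0.09/0.91) = 15.2. The ratio implied by the multivariate interval, 32.4, is about twice that.

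**5. Counts behind 60% and 9%.** Up to 30 participants, a group that rounds to 60% must have a size that is a multiple of 5, and one that rounds to 9% must have size 11, 22 or 23. The possible totals are therefore 5 + 11 = 16, 10 + 11 = 21, 15 + 11 = 26, 5 + 22 = 27 and 5 + 23 = 28. None is 29 or 30.

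| Table | Fisher p | Logistic Wald p |
|---|---|---|
| 3/5 vs 1/11 | 0.063 | 0.051 |
| 6/10 vs 1/11 | 0.024 | 0.028 |
| 9/15 vs 1/11 | 0.014 | 0.021 |
| 3/5 vs 2/22 | 0.030 | 0.021 |
| 3/5 vs 2/23 | 0.027 | 0.019 |

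Four of the five give 0.02 by one test or the other, so the table cannot be recovered. With looser rounding, 11/19 vs 1/11 (57.9% vs 9.1%) and 12/20 vs 1/10 (60% vs 10%) use all 30. The text also leaves open whether the percentages are collection rates by AT group or the share with AT ≤ 14 by collection status.

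**6. Multiplicity, with the number of tests assumed.** Bonferroni: 3 × 0.02 = 0.06 (0.045 to 0.075, because 0.02 is rounded); 7 × 0.02 = 0.14; 9 × 0.02 = 0.18.

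**The case against.** The strongest reply is that the document already concedes the study's limits. Item 5 names the retrospective design and small CPET group and calls for a larger prospective study. Collection and AT are both listed in the plan, and the Background cites an earlier study linking CPET to abscess. The association has a multivariate as well as a univariate p of 0.02. All of that stands. It would be wrong to say that the document carries no caveat, or that the p-value is unadjusted in every sense; it is not adjusted for multiplicity. The caveat concerns design and numbers, though, and does not mention the cut-off or the testing. The cited study is a reason to look at abscess, but the Background gives none for 14.

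Some stronger inferences are tempting and not supported:

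- *That 14 was picked from the data, or that every CPET item was tested against every complication.* The document says neither. Estimating the error rate of a cut-off search would mean guessing the counts and the direction of the percentages.
- *That the model is sound because interval and p agree.* Agreement shows only that they are consistent with one Wald calculation. With an implied ratio twice the crude one and an upper limit of 657, sparse-data bias cannot be ruled out. It is not demonstrated either.
- *That HR is a mislabelled odds ratio.* This is plausible, since binary logistic regression is the only regression named and no time-to-event analysis is described. But the sentence on CPET measures names no model.
- *That CPET participants were left out.* The percentages may simply be imprecise.
- *That the chemotherapy sentence has no possible basis.* No chemotherapy item is listed among the data, but one cited study's title concerns non-progression to adjuvant therapy, so a citation might support it.

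**Conclusion.** The point holds in two parts of different strength.

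The reporting error is clear, and confidence is high. HR 3.5, 1.6–657 and p = 0.02 cannot all be right. If the interval is right, the ratio is about 32.4 and the printed value is too small by a factor of about nine. This rests on a Wald interval; the exact-interval comparison does not rescue 3.5. Reading 3.5 as the log coefficient is the explanation that fits, pending the model output. Even when corrected, the estimate is extremely imprecise.

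The overstatement is real, with moderate confidence. Item 8 presents as established an association in a subgroup of at most 30, at a cut-off with no stated unit or origin and with no multiplicity control described. How far the error rate is inflated depends on facts not reported: p = 0.02 would become 0.06 for three tests, 0.14 for seven and 0.18 for nine under Bonferroni. The data can support a hypothesis about AT, but not a cut-off. They do not show that the association is false.

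**What to change.** 1. Correct the ratio and its interval from the model output. State which model was fitted, whether the ratio is a hazard or odds ratio, and the covariates.
2. Restate the conclusion as an exploratory association in the CPET subgroup, not adjusted for multiplicity, with the cut-off needing validation. Support the chemotherapy sentence with data or a citation, or remove it.
3. Report the 2×2 counts, what 60% and 9% are percentages of, how many of the 30 had a usable AT value, the unit and origin of 14, and the number of CPET-by-complication tests run.

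Optional: a sensitivity analysis with AT as a continuous variable, using Firth or exact logistic regression. It assumes linearity on the log-odds scale, which so few events cannot check.

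The cost is small: revised wording, one corrected ratio and counts from data already held, plus a few hours for the optional analysis. The downside is that the headline claim becomes weaker.

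### Anaerobic threshold is reported and concluded on only as ≤14 versus >14, an unexplained split that probably discards a quarter to a half of the information in a very small CPET group

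*Combined protocol and SAP*

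**What the plan says.** The list of CPET-specific data under Baseline Characteristics includes "Anaerobic threshold" with no unit and no categories. Items in the same list that were collected as categories (ST ischaemia, pulmonary function) have their categories printed beside them.

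The statistical overview under Outcome Measures says that univariate and multivariate analyses examined whether CPET measures predict complications. It does not say how any CPET measure was coded, and it gives no cut-point or rule for choosing one.

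In section 8 the measure appears only as a two-level factor:

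- Group size: "CPET was performed in 30 participants (21"%.
- Finding: "Anaerobic Threshold (AT) ≤ 14 on CPET was a risk factor to develop intra-abdominal collection".
- Unadjusted result: "univariate analysis (60% Vs 9%, p-value 0.02".
- Adjusted result: "HR 3.5, 95% CI 1.6-657, p-value 0.02".

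The closing conclusion uses the same split: "participants who have Anaerobic Threshold ≤ 14 on CPET, are more likely to develop intra-abdominal collection requiring drainage after Pancreatoduodenectomy". No effect per unit, no risk curve and no counts on either side of 14 are given.

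**The concern.** The study asks whether CPET measures identify participants at risk. A split at 14 treats someone just below the line as different from someone just above it, and as the same as someone far below it. If risk changes gradually with anaerobic threshold, that discards usable information and hides the shape of the relation, wherever the cut is placed.

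The cost matters because at most 30 participants contribute. Every 2×2 table that fits the reported percentages has only one or two events in the >14 group, so the ratio is fragile. The conclusion is also worded as though 14 marks a boundary in risk, and a two-group comparison cannot show that.

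**Working it through.** **Inputs.** From section 8: 30 CPET participants; collection rates of 60% and 9%; p = 0.02; interval 1.6 to 657. From the statistical overview: significance at 0.05. The documents do not give the counts either side of 14, the test used or the distribution of anaerobic threshold. These are handled below as assumptions with ranges. The percentages are read as event rates within each anaerobic threshold group.

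**Step 1: reproduce the reported comparison.** All 2×2 tables with a total of 14 to 30 that round to 60% and 9% were listed, and each was tested by Fisher's exact test and by chi-square with and without continuity correction.

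| ≤14 | >14 | Total | Fisher p | Chi-square p | Corrected chi-square p |
|---|---|---|---|---|---|
| 3/5 | 1/11 | 16 | 0.063 | 0.029 | 0.120 |
| 6/10 | 1/11 | 21 | 0.024 | 0.013 | 0.045 |
| 9/15 | 1/11 | 26 | 0.014 | 0.008 | 0.026 |
| 3/5 | 2/22 | 27 | 0.030 | 0.008 | 0.045 |
| 3/5 | 2/23 | 28 | 0.027 | 0.007 | 0.038 |

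Only 6/10 versus 1/11 gives 0.02 to two decimals, by Fisher's test. No matching table totals 30.

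For that table the crude odds ratio is (6 × 10)/(4 × 1) = 15. The standard error of its log is √(1/6 + 1/4 + 1/1 + 1/10) = 1.23, so the Wald 95% interval is exp(2.71 ± 1.96 × 1.23), about 1.3 to 168. The single event in the >14 group contributes 1.00 of the variance of 1.52.

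**Step 2: information lost, small effect.** For a normal predictor with a small linear effect, a split that puts a share q on one side keeps φ(z_q)²/[q(1 − q)] of the information held by the linear term.

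- 10/21: 0.3982²/0.2494 = 0.636, a loss of 36.4%.
- 15/26: 0.3915²/0.2441 = 0.628, a loss of 37.2%.
- 5/16: 0.3540²/0.2148 = 0.583, a loss of 41.7%.
- 5/27: 0.2671²/0.1509 = 0.473, a loss of 52.7%.
- 5/28: 0.2611²/0.1467 = 0.465, a loss of 53.5%.

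**Step 3: information lost at the reported effect.** 60% versus 9% is not a small effect. A logistic model in the measured value was calibrated so that the average risk on each side of the split is 60% and 9%. The loss is 1 minus the ratio of the expected log-likelihood gain from the split to that from the value. At 10/21 with normal values the slope is 2.16 per SD and the loss is 31.4%. Over the five splits the loss is 29% to 36% with normal values, and 25% to 38% when uniform and lognormal shapes are included.

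**Step 4: sensitivity to shape.** With a small effect, uniform values give a loss of 25.2% at 10/21, and a skewed lognormal (log-SD 0.3) gives 67.0% at 5/28. If risk is flat on each side and jumps at 14, the loss is zero.

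**Step 5: power.** Simulated with normal values, a split near the middle and about one third of participants having events, comparing the value with an uncorrected chi-square on the split:

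| Odds ratio per SD | n | Value | Split |
|---|---|---|---|
| 3 | 21 | 51% | 38% |
| 3 | 30 | 66% | 49% |
| 8.6 (about the reported effect) | 21 | 89% | 74% |
| 8.6 | 30 | 97% | 88% |

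The value does better in each setting. The odds ratio of 3 is an illustrative assumption and is not taken from the documents.

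**The case against.** Section 8 is a short summary. A reader might infer that anaerobic threshold was analysed only as a split, but the documents show only that it was reported that way. They do not say whether a continuous analysis was also run. That it was recorded as a number is likewise an inference, though a strong one: the list prints categories where they exist, and a participant cannot be placed at or below 14 without a value.

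A reader might also put the loss at 36% to 53% of 30 participants. That range needs normal values, a small effect and a split the documents do not report, and its two ends come from different tables. The 53% end needs 5 of 27 or 28 at or below 14, which does not reproduce p = 0.02. Nor is 30 the right base, because no matching table totals 30. On the table that does reproduce p = 0.02, 36.4% of 21 is about 8 participants.

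Continuous coding does not promise a stable estimate. In simulation at the reported effect with n = 30, a one-predictor continuous fit still had a median upper-to-lower interval ratio of about 38. The printed interval has a ratio of 657/1.6, about 410, but it is an adjusted estimate, so the split cannot be blamed for all of that width.

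The result is a subgroup finding on a secondary outcome, and the Limitations section concedes that the CPET group was small. Both points are fair and limit the priority. Neither justifies the split, and a small group makes avoidable loss matter more.

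Continuous coding also leaves separate problems untouched. The unexplained denominators remain, and the printed ratio of 3.5 does not fit its own interval: the geometric midpoint is √(1.6 × 657) = 32.4, and its natural log is 3.48.

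**Conclusion.** The concern holds in a limited form. Anaerobic threshold is reported and concluded on only at ≤14 versus >14, and the plan gives no cut-point and no reason for splitting. With roughly normal values and a smooth relation with risk, the likely loss is roughly a quarter to a half. The best-supported figures are about 36% (small effect) and about 31% (reported effect), both on 6/10 versus 1/11. A strongly skewed distribution with an uneven split could push the loss higher, and a true step at 14 would make it zero. The documents offer no evidence of such a step.

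A reader might go further and conclude that the association is false, or that 14 was picked from these data. The documents do not say how 14 was chosen, and this check does not test either claim. What it supports is a less efficient analysis than the data allow, and a conclusion that treats 14 as a boundary without evidence for one.

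**What to change.** Make the continuous form the main analysis of anaerobic threshold, VO₂ peak and VE/VCO₂: a logistic odds ratio per unit and per SD with its 95% interval, a plot of predicted risk against the value, and a simple check for non-linearity where the data allow. State the unit, the number analysed and the counts with and without a collection on each side of 14. Keep ≤14 versus >14 as a descriptive comparison only, say how 14 was chosen, and reword the conclusion to follow the continuous result. If a continuous analysis has already been run, report it.

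The cost is one re-fit of data already held and some changes of wording. There is a small downside: a linear term assumes that log-odds change linearly with the value, and so few events allow only a weak check of that. The estimate will use the data better but will remain imprecise, and the text should say so.

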3 THEORETICAL FRAMEWORK

4 RESEARCH QUESTION/AIM(S)

Objectives: To assess if pre-operative cardiopulmonary exercise testing is useful and effective in predicting at risk participants for post-operative morbidity and mortality, who undergo Whipple's surgery.

DATA ELEMENTS

1. Participant flow

Recruitment Details:

Participants for the study will be identified from a prospectively maintained database, by database search from April 2016 to March 2020, online records, clinical portal and Somerset cancer registry. Duplicates will be removed, cases will be screened.

This is a single centre study, to be done at, Royal Blackburn Hospital, East Lancashire Hospitals NHS trust, a District general Hospital in North of England. The study will be carried out in the department of General and HPB surgery, in liaison with Department of anaesthesia. This is the HPB referral centre for Lancashire and South Cumbria and incorporates participants referred for pancreatic surgery from three hospital trusts (Lancashire Teaching, University Hospital Morecambe Bay and Blackpool Teaching Hospitals).

Arm/Group Information:

The study will have two groups of participants, one who have undergone CPET pre-operatively and the other who have not undergone CPET.

Group 1 – Participants who have undergone CPET as a part of pre-operative assessment as well as P-POSSUM score calculation for predicting post-operative morbidity and mortality.

P-POSSUM is a scoring system for general elective and emergency surgeries which takes into account various physiological and operative parameters to calculate risk of morbidity and mortality in terms of percentages.

Group 2 – Participants who have not undergone CPET as a part of pre-operative assessment rather have only P-POSSUM calculated for predicting post-operative morbidity and mortality.

Period of Overall Study:

The study was conducted from February 2021 to March 2022. The database search was conducted and data collated. The study was conducted in one stage over a year.

Participants:

143 participants were recruited for the study during a period of 1 year. Out of 143 participants, 30 participants had undergone CPET as a part of pre-operative assessment.

2. Baseline Characteristics:

Baseline Analysis Population Information:

Data on baseline characteristics included age, sex, comorbidities, Rockwell frailty score, ASA grade, BMI.

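### The conclusion states that the low anaerobic threshold group will start chemotherapy later, but no chemotherapy data, outcome or analysis is listed or reported

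*Combined protocol and SAP*

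**What the plan says.** The conclusion in section 8 (Results of the study) has two sentences. The first reads, in part, "By this study we concluded that participants who have Anaerobic Threshold ≤ 14 on CPET, are more likely to develop intra-abdominal collection requiring drainage". The second, which closes the document, reads "This group of participants will be less likely to start chemotherapy early".

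The rest of the document sets out what was studied:

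- **Objective** (4 Research question/aim(s)): "To assess if pre-operative cardiopulmonary exercise testing is useful and effective in predicting at risk participants for post-operative morbidity and mortality", in patients having a Whipple's operation.
- **Baseline data** (2. Baseline Characteristics): "Data on baseline characteristics included age, sex, comorbidities, Rockwell frailty score, ASA grade, BMI".
- **Study-specific data** (same section): "Data on study specific characteristics included dates of admission and discharge, diagnosis, details of surgery undergone, details of morbidity using Clavien-Dindo classification and mortality". CPET measures and P-POSSUM scores were also collated.
- **Outcomes** (3. Outcome Measures): mortality at three time points, and nine named complications.
- **Analysis** (Statistical analyses overview): predicted against actual mortality and morbidity, and CPET measures as predictors of complications and morbidity.
- **Data sources** (1. Participant flow): a prospectively maintained database, with "online records, clinical portal and Somerset cancer registry", named as the means of identifying participants.

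**The concern.** The closing sentence is a flat prediction about the timing of chemotherapy in the group with AT of 14 or below. It stands under a results heading, directly after a sentence introduced as the study's conclusion, and shares that sentence's subject. Nothing tells the reader that the basis has moved from a reported analysis to something else.

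This matters because it is half of the stated conclusion. The document was amended for submission to a public registry, and a reader of that record may have little more than this paragraph. Such a reader could take a later start of chemotherapy as something observed in these patients.

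**Working it through.** The document gives no chemotherapy figure, so there is nothing to reproduce. The check is whether any listed variable, outcome, analysis or result could support the sentence.

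**1. Listed outcomes (3. Outcome Measures).**
- Mortality: in hospital, 30 days, 90 days = 3 items.
- Morbidity: pancreatic fistula, biliary fistula, delayed gastric emptying, bleeding, intra-abdominal collection, renal failure, cardiac, pulmonary, pulmonary embolism/DVT = 9 items.
- Total 3 + 9 = 12. Items naming chemotherapy or adjuvant therapy: 0.

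**2. Listed data items (2. Baseline Characteristics and the CPET list that follows).**
- Baseline: 6.
- Study-specific: 5 (admission and discharge dates counted as one).
- CPET: 7.
- P-POSSUM scores: 1.
- Total 6 + 5 + 7 + 1 = 19. Items naming chemotherapy receipt, date or eligibility: 0. Splitting compound items would raise the total but leave the numerator at zero.

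**3. Reported results (section 8).** The paragraph gives the cohort size, the number with CPET, age, the frequency of intra-abdominal collection, AT as a risk factor for collection, and pancreatic leak as another. The only outcome reported against AT is collection. No chemotherapy count, estimate, interval or test appears.

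**4. What the sentence would need.** The claim requires a definition of an early start, the number of patients for whom chemotherapy was intended, and the split of that number by AT group. None is given. The cohort is defined by operation and dates, so the number of candidates for chemotherapy cannot be read from it.

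**5. Whether the claim follows from the reported finding.** To get from AT to chemotherapy timing by way of collection takes two links:
- AT of 14 or below to more collections: reported.
- Collection to a later start of chemotherapy: neither stated nor tested.

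Two associations would not by themselves establish a third, and here only one is reported.

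**6. How firm the first link is (context only; this concerns collection).** It comes from the CPET subgroup, 30/143 = 21.0%, which matches the stated 21%. The result is given as "multivariate analysis (HR 3.5, 95% CI 1.6-657, p-value 0.02".
- Ratio of limits: 657/1.6 = 410.6, so the upper limit is about 411 times the lower.
- Geometric midpoint: √(1.6 × 657) = √1051.2 ≈ 32.4, whose natural log is about 3.48. A Wald-type interval for a ratio would be centred near 32, not 3.5. The stated 3.5 may be the log coefficient, so it needs checking in its own right.

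**7. Other text near the topic.** The title of reference 3 mentions non-progression to adjuvant therapy. That is an earlier external study. Section 1 (Background) describes it only for fistula, abscess and length of stay, and it is not cited at the conclusion. Not progressing to adjuvant therapy is also a different outcome from starting it later.

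**The case against.** The strongest reply is that the sentence is an inferred clinical implication and not a claimed result. Results in section 8 are in the past tense, the phrase introducing the conclusion governs only the collection sentence, and the last sentence turns to the future. A collection that needs drainage is a plausible reason for delay, and reference 3 shows that the topic was in the authors' literature. This reading is open, and it stands to that extent. But the sentence is not marked as an implication, and it is neither hedged nor cited.

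Second, absence from the summary does not prove absence from the data. The data lists are worded as inclusions, a cancer registry was among the sources, the flow chart is not shown, and the results paragraph is selective: it gives no mortality result although mortality is the primary outcome. This also stands. The supportable statement is that chemotherapy is not listed or reported, not that it was never looked at.

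Third, the limitations could be said to cover the point: "A prospective study with a large sample size is required to obtain more reliable results". That is a general caveat about small numbers. It does not tell the reader that one of the two conclusions concerns an outcome with no reported data.

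Finally, this is a wording fault in a completed retrospective study and changes no estimate. That is true and limits its seriousness. It does not make it clerical, because it alters what the study is said to have concluded.

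**Conclusion.** The concern holds. One of the two concluding sentences makes an unhedged, uncited statement about chemotherapy timing that nothing listed or reported for this cohort supports: 0 of 12 outcome items, 0 of 19 data items and no reported result. No effect size can be put on the claim, because no estimate, denominator or definition of early is given. The outcomes and reported estimates are untouched.

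This rests on the text as available. If chemotherapy data were collected but not listed, the statement might have a basis, but that basis is not shown. The point should be fixed; it does not call the design or the analysis into question.

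**What to change.** Delete the final sentence of section 8, or reword it as a hypothesis not assessed in the reported analyses, with a citation if an external study is its basis. Limit the conclusion to the outcomes in section 3 (Outcome Measures).

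If chemotherapy data were in fact collected and the authors wish to report them, label the comparison by AT group as post hoc and exploratory. Define what counts as an early start and who was eligible, and give the number in each AT group and the estimate with its 95% confidence interval.

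The first route costs one sentence and needs no reanalysis. The second costs one additional exploratory analysis, and only if the data exist.
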